18.1.12.1 Overall post-baseline value

For the shift table and PCI frequency table of laboratory, vital signs and ECG parameters, an overall post-baseline value will be derived. Therefore, all post-baseline assessments, including unscheduled assessments, are taken into account.

For the overall post-baseline summary subjects might have both low and high values. These subjects will be categorized in a new category “high and low” and excluded from the categories “high” and “low”. The inclusion of this category in the frequency and shift tables is only required if there are any subjects falling into this category.

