1.2.2 Part 2: Tapentadol Period

Visit Day (range)	Tapentadol Period														ET ^{bc}	F12M ^b	F7D ^d
	M1 ^a	M2 ^a	28 (±5)	56 (±5)	84 (±5)	112 (±5)	140 (±5)	168 (±5)	196 (±5)	224 (±5)	252 (±5)	280 (±5)	308 (±5)	336 (±5)			
Record concomitant medication intake/therapies	X	X	X	X	X	X	X	X	X	X	X	X	X	X	X	X	X
Perform physical examination															X ^e	X ^e	X ^e
Record height					X			X			X			X	X	X	
Record body weight			X	X	X	X	X	X	X	X	X	X	X	X	X	X	X
Record vital signs	X	X	X	X	X	X	X	X	X	X	X	X	X	X	X	X	X
Complete questionnaires ^f - Modified constipation assessment scale - Subjective opiate withdrawal scale															X	X	X ^g
Record "pain right now" in CRF (VAS, FPS-R)	X	X	X	X	X	X	X	X	X	X	X	X	X	X	X	X	X ^g
Take blood for central laboratory				X			X		X		X		X	X	X	X	
Collect urine/perform dip stick urinalysis (safety laboratory)					X			X			X		X	X	X	X	
Perform urine pregnancy test ^h						X		X			X		X	X	X	X	
Train/instruct subject how to use diary to record intake of IMP, including time of administration.	X	X	X	X	X	X	X	X	X	X	X	X	X	X			

 Protocol KF5503-66
 including Amendment 05

 Page 16 of 137
 DMS version 9.0
 27 Jul 2017

Period	Tapentadol Period															ET ^{bc}	F12M ^b	F7D ^d
	Visit	M1 ^a	M2 ^a	TP1	TP2	TP3	TP4	TP5	TP6	TP7	TP8	TP9	TP10	TP11	TP12			
				7 (± 2)	14 (± 2)											Day (range)		
Check diary compliance	X	X	X	X	X	X	X	X	X	X	X	X	X	X	X	X	X	
Collect diary																	X	X
Collect returned IMP	X	X	X	X	X	X	X	X	X	X	X	X	X	X	X	X	X	X
Perform drug accountability ⁱ	X	X	X	X	X	X	X	X	X	X	X	X	X	X	X	X	X	X
Dispense IMP	X	X	X	X	X	X	X	X	X	X	X	X	X	X	X			
Discuss IMP titration/dose adjustment	X	X	X	X	X	X	X	X	X	X	X	X	X	X	X			
Train/instruct subject, parent(s), guardian(s), or caregiver on IMP use. Exchange instruction sheet if necessary (e.g., due to weight change)		X	X	X	X	X	X	X	X	X	X	X	X	X	X			
Assess/record adverse events	X	X	X	X	X	X	X	X	X	X	X	X	X	X	X	X	X	X
Check discontinuation criteria for IMP intake	X	X	X	X	X	X	X	X	X	X	X	X	X	X	X			
Complete end of trial tasks, e.g., collect subject trial cards																		X

Days are referenced by last intake of IMP in Part 1.

- a) Visit M1 and Visit M2 are only for subjects who were allocated to morphine PR in the Treatment Period.
- b) If Visit F12M and Visit ET are performed on the same day, assessments scheduled for both visits will not be repeated at Visit F12M.
- c) Visit ET must be performed within 3 days after last intake of IMP if IMP is stopped before Visit F12M in Part 2.

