8 ANALYSIS CONVENTIONS

8.1 General principles

Analysis structure

Separate analyses will be performed for Part 1 and Part 2.

The analysis for Part 1 will take into consideration the Treatment Period of Part 1. For Part 1, all presentations will be done per treatment arm, i.e., comparing the tapentadol arm to the morphine arm.

The analysis for Part 2 will take into consideration the Tapentadol Period and Observation Period of Part 2. Given that the different periods, i.e., Tapentadol Period and Observation Period, are not comparable, due to the heterogeneity of the populations (see Section 18.1.3 for additional information), all analyses of Part 2 will be illustrated separately for the Tapentadol and Observation Period as detailed below, if not specified differently.

For the Tapentadol Period, all statistical analyses will be presented by the following arms:

- Subjects in the Tapentadol Period pretreated with morphine during Part 1.
- Subjects in the Tapentadol Period pretreated with tapentadol during Part 1.
- All subjects in the Tapentadol Period.

For the Observation Period, all statistical analyses will be presented by the following arms:

- Subjects pretreated with morphine during Part 1 and continuing the trial in the Observation Period directly after Part 1.
- Subjects pretreated with tapentadol during Part 1 and continuing the trial in the Observation Period directly after Part 1.
- All subjects continuing the trial in the Observation Period directly after Part 1.
- Subjects discontinuing the Tapentadol Period before F12M and continuing the trial in the Observation Period.

Unless otherwise specified, descriptive summaries will be provided for each time point and for the change from baseline (defined in Section 8.2.2) to each time point. Additionally, for Part 2, the last assessment (defined in Section 8.2.2) and change from baseline to the last assessment will be summarized.

Data presented in subject data listings will be sorted by treatment if not specified differently.

Unscheduled measurements of laboratory parameters, vital signs and electrocardiogram will be presented in the subject data listing. In general, unscheduled measurements will not be included in the analysis. However, they will be considered in the derivation of the overall post-baseline value (see Section 18.1.12.1) that is used in the shift and alert frequency analyses.

Details on the programmatic derivation of the trial periods can be found in Section 18.1.2.10.

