12 EXPOSURE AND COMPLIANCE

12.1 Exposure

IMP intake is assessed in the eDiary as well as the drug accountability page of the eCRF. Unless specified differently, analyses described below will be based on data collected in the eDiary.

Part 1

The daily doses of IMP per kg body weight will be determined for each subject and summarized descriptively for each calendar day of the Treatment Period.

A graphical illustration will illustrate the means and 95% confidence intervals of the daily doses of IMP per kg body weight (Tapentadol equivalents; 1 mg morphine PR is equivalent to 2.5 mg tapentadol PR) of each day separately for the two treatment arms.

The duration of exposure will be summarized descriptively. Duration of exposure of Part 1 is defined as:

Date of last IMP administration in Part 1 – Date of first IMP intake +1

Furthermore, the overall average daily dose per kg body weight will be determined for each subject and summarized descriptively. This analysis will be based on data assessed via drug accountability collected in the eCRF.

Part 2

Exposure to IMP is only assessed during the Tapentadol Period and analyses of exposure of Part 2 will only be presented for the Tapentadol Period.

The average daily doses and modal (i.e., most frequent) doses of IMP per kg body weight will be determined for each four-week interval between two visits (excluding visits M1 and M2) and summarized descriptively per interval. In case of more than one modal dose value for an interval, the average of those will be considered.

For a detailed definition of the time intervals and how to handle subjects terminating the Tapentadol Period in between two scheduled visits, see Section 18.1.6.

A graphical illustration will illustrate the means and 95% confidence intervals of the average daily doses of IMP of each interval for the two arms of differently pretreated subjects.

The duration of exposure will be summarized descriptively. Duration of exposure of Part 2 is defined as

Date of last IMP administration in Part 2 – Date of first IMP intake in Part 2 +1

Furthermore the overall average daily dose per kg body weight will be determined for each subject between visit VE and visit ET/F12M and summarized descriptively. This analysis will be based on data assessed via drug accountability collected in the eCRF.

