15.2.3 Vital signs

Vital signs measured in the trial are respiratory rate, systolic and diastolic blood pressure and pulse rate.

For each parameter of the vital signs, observed values will be summarized by visit. In addition changes from baseline for all post-baseline visits will be summarized.

Shift tables from baseline for the different visits and overall (worst value on treatment, see Section 18.1.12.1 for definition of worst) will be generated for each vital sign parameter for categories low, normal and high, based on the reference ranges, defined by the sponsor, in Table 9.

Furthermore, a summary by visit and overall post-baseline will be provided on the number and percentage of subjects with alert value results. Alert values are abnormally low or abnormally high measurements regarded as potentially clinically important values defined by the sponsor (Table 10). See Section 18.1.12.1 for details regarding the analysis.

For Part 1, graphical presentations over time of the trial for the observed data will be provided (mean and 95% confidence interval), including numbers on the top and the bottom of the plot representing the number of subjects and the frequency of subjects with abnormally high/low values (based on Table 10) by treatment arm and visit.

For the Tapentadol Period, graphical presentations over time of the trial for the observed data will be provided (mean and 95% confidence interval), including numbers on the top and the bottom of the plot representing the number of subjects and the frequency of subjects with abnormally high/low values (based on Table 10) by visit and the two arms of differently pretreated subjects.

A listing of subjects with vital sign results outside the sponsor defined alert ranges will be provided ([Table 10](#)).

All vital signs values will be presented in the subject data listing of the respective part. Values out of normal ranges ([Table 9](#)) will be flagged as H (above the normal range) or L (below the normal range) in the listing. If a value classified as high or low is in addition also out of alert ranges, it will be flagged as H* or L* in the listing.

Table 9: Normal ranges of vital signs

Parameter (unit)	Age class			
	6 - <9 years	9 - <12 years	12 - <16 years	16 - <18 years
Diastolic BP (mmHg)	57-71	60-75	64-78	65-81
Systolic BP (mmHg)	95-110	101-116	108-121	109-127
Heart rate HR (bpm)	74-111	67-103	62-96	58-92
Respiration rate	18-24	16-22	15-21	13-19

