18.1.12 Laboratory, vital signs and ECG parameters

Age determined at Visit V2/VE for Part 1/Part 2, respectively will be used for all reference ranges throughout the trial.

Ordering of parameters

Laboratory parameters, vital signs and ECG parameters will be ordered alphabetically within their parameter group (e.g., hematology, clinical chemistry, and urinalysis). Visits will be sorted chronologically. If changes from BL are displayed by visit all visits will be displayed first followed by all the changes from baseline.

Not exact values

Not exact laboratory values such as < x, > x will not be included in the analysis of continuous parameters. The frequency of occurrence of not exact values will be displayed in the respective table where applicable.

Categorical parameters

For categorical parameters, 2 types of tables are created:

1. Frequency tables display the pre-defined categories by visit and overall post-baseline.
2. Shift tables display the shift from baseline at each visit and overall.

Both types of tables show the number of subjects still in the trial (n) at the visit and the number of missing values (nMiss) at the visit. For the overall presentation, all post-baseline values on treatment are taken into account and nMiss is the number of subjects without any on-treatment post-baseline values.

In tables where parameters are classified as abnormal low, normal, abnormal high based on reference ranges, and alert low, normal, alert high based on sponsor-defined alert ranges the available pre-defined categories must be displayed in tables even if there are categories to which no subjects belong. Categories that are not applicable must be omitted.

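### The Tapentadol Period 'overall post-baseline' vital-sign row gives morphine-pretreated children two extra assessments, and the SAP states conflicting rules for what that row contains

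*SAP*

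**What the plan says.** **The pooling rule.** For the shift and alert tables of laboratory, vital-sign and ECG parameters, SAP 18.1.12.1 derives an overall value in which "all post-baseline assessments, including unscheduled assessments, are taken into account". A child with both low and high values leaves the 'high' and 'low' categories and goes into a category 'high and low'.

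**The visits.** A footnote to the schedule in Protocol 1.2.2 states that "Visit M1 and Visit M2 are only for subjects who were allocated to morphine PR in the Treatment Period". Protocol 11.1.2.1 lists vital signs at both visits, but no laboratory test or ECG.

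**The columns.** SAP 8.1 shows the Tapentadol Period by pretreatment, one column being "Subjects in the Tapentadol Period pretreated with morphine during Part 1". For vital signs, SAP 15.2.3 plans "a summary by visit and overall post-baseline will be provided on the number and percentage of subjects with alert value results".

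**The competing rules.** SAP 18.1.12, immediately before the pooling rule, reads: "For the overall presentation, all post-baseline values on treatment are taken into account". It counts a child with no on-treatment value as missing. For its shift tables SAP 15.2.3 describes the overall entry as "worst value on treatment, see Section 18.1.12.1 for definition of worst", and 15.2.2 does the same for ECG. SAP 18.1.12.1 contains no definition of 'worst'.

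**The concern.** A row that counts a child once any value is out of range depends on how often the child is measured. Here the number of measurements differs by column because of the schedule. M1 and M2 exist because withdrawal symptoms may follow the change from morphine to tapentadol, so an excess produced by the extra visits would appear where a reader expects a transition effect. The only Part 2 objective is to describe long-term safety, and no between-arm safety tests are planned (SAP 15), so the table will be judged by eye.

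The conflicting window rules are a second problem. Two programmers following the SAP could fill the same row with different values and both be in line with the text.

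**Working it through.** The plan states no alert rate, so there is no figure of its own to reproduce.

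**Inputs from the documents.** Scheduled vital signs after baseline (Visit VE) in the Tapentadol Period, from Protocol 1.2.2 and 11.1.2:

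| Child | Tapentadol-pretreated | Morphine-pretreated |
|---|---|---|
| Completer: TP1–TP12, F12M | 13 | 15 |
| Stops after TP3: TP1–TP3, ET | 4 | 6 |
| Stops after TP1: TP1, ET | 2 | 4 |

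**Assumption, not in the documents.** The alert probability p per visit is the same in both columns, and is varied from 1% to 20%. For pulse it may not be small: as printed, the heart-rate alert limits in SAP Table 10 equal the normal limits in Table 9 for ages 6 to under 16.

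**Any alert, independent visits.** P(any) = 1 − (1 − p)^k. For a completer at p = 5%: 1 − 0.95^13 = 48.7% and 1 − 0.95^15 = 53.7%.

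| p | Completer, 13 v 15 | Stop after TP3, 4 v 6 | Stop after TP1, 2 v 4 |
|---|---|---|---|
| 1% | 12.2% v 14.0% | 3.9% v 5.9% | 2.0% v 3.9% |
| 5% | 48.7% v 53.7% | 18.5% v 26.5% | 9.8% v 18.5% |
| 10% | 74.6% v 79.4% | 34.4% v 46.9% | 19.0% v 34.4% |
| 20% | 94.5% v 96.5% | 59.0% v 73.8% | 36.0% v 59.0% |

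**Any alert, correlated visits.** Values within a child are unlikely to be independent. In a beta-binomial model with correlation ρ, set s = 1/ρ − 1, a = ps and b = (1 − p)s. Then P(any) = 1 − Π (b + i)/(s + i) for i = 0 to k − 1. At p = 5%:

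| ρ | Completer, 13 v 15 | Stop after TP3, 4 v 6 |
|---|---|---|
| 0.2 | 27.0% v 28.6% | 14.4% v 18.4% |
| 0.4 | 17.9% v 18.8% | 11.3% v 13.5% |

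**'High' taken alone.** With probability p on each side, P(high only) = (1 − p)^k − (1 − 2p)^k and P(both) = 1 − 2(1 − p)^k + (1 − 2p)^k. For completers with independent visits:

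- p = 5% per side: high only 25.9% v 25.7%.
- p = 10% per side: high only 19.9% v 17.1%, both 54.7% v 62.3%.

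Two more visits can therefore lower the 'high' or 'low' row, because children move to 'high and low'.

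**Common visits only.** Counting TP visits and ET/F12M gives 13 v 13, 4 v 4 and 2 v 2. The excess due to M1 and M2 is then zero at every p and ρ.

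**The window rules side by side.**

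- *F7D.* It takes place 7 ± 2 days after the last dose. The earliest, day 5, is 120 hours, beyond the 72 hours that SAP 8.2.2 allows. These vital signs are post-baseline but not on treatment, so 18.1.12 leaves them out while 18.1.12.1 has no such limit.
- *Observation Period.* SAP 8.2.2 defines on-treatment time for Part 1 and the Tapentadol Period only, and SAP 18.1.3 confirms that no trial drug is given in the Observation Period. Vital signs and laboratory tests are scheduled there at OPx or F12M. Under 18.1.12.1 those values fill the overall row. Under 18.1.12 only a reading within 72 hours of the last dose could count, so nearly every child would be missing.

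**The case against.** The strongest case on the other side is that this is a wording repair. SAP 7.2.2 explains that 'high and low' replaced 'worst', so the 'worst' references are leftovers and the intent is clear. Sections 18.1.12 and 18.1.12.1 can be read together for the treated periods, one giving the window and the other admitting unscheduled values. Visits VE (after early stopping) and ET must fall within 3 days of the last dose, so the two windows differ there mainly in late values. In the Observation Period each child has one scheduled vital-sign value, which also appears by visit and as the last assessment. Vital signs are tabulated and plotted by visit and pretreatment arm, so a careful reader can see M1 and M2 separately. All per-visit risks are assumed, and no 12-week overall row is planned: the interim Part 2 analysis uses all data then available.

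Most of this stands, and it limits the point to a descriptive summary. It does not remove the unequal counts from the overall row, nor tell a programmer which window applies to F7D or the Observation Period.

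A reader might also infer that the authors had already judged M1 and M2 non-comparable, because SAP 12.1 summarises dose for "each four-week interval between two visits (excluding visits M1 and M2"). That does not follow. SAP 18.1.6.2 drops them only as interval boundaries: the first interval runs from VE to TP1, so those weeks stay in the exposure data.

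**Conclusion.** The point holds for one output, the overall vital-sign row of the Tapentadol Period, and for 'any alert' in that row. The direction follows from the schedule alone, given equal per-visit risk and equal follow-up. The size rests on assumed risks. At p = 5% with independence it is 5 points for completers and 8 points for children stopping after TP3; with correlation 0.2 to 0.4 the completer gap is about 1 to 2 points. The conflict between 18.1.12, 18.1.12.1, 15.2.2 and 15.2.3 is a matter of text and needs no assumption.

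Stronger readings that the documents do not support:

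- *That every overall row is inflated.* M1 and M2 include no laboratory tests, ECG is recorded in Part 1 only, and Part 1 has no such visits. The 'high' and 'low' rows can move either way.
- *That the Observation Period rows are empty.* They are practically all missing only if 18.1.12 overrides 18.1.12.1.
- *That efficacy conclusions are touched.* The table is descriptive and the primary analysis does not use it.

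**What to change.** 1. State one window per period, in the same words, in SAP 18.1.12 and 18.1.12.1. For the Treatment and Tapentadol Periods use the on-treatment period of SAP 8.2.2: last dose plus 72 hours, or the cut at VE defined there for children continuing into the Tapentadol Period. For the Observation Period use all values after that period's baseline.
2. Delete the references to 'worst' in SAP 15.2.2 and 15.2.3.
3. For Tapentadol Period vital signs, keep the overall row with all assessments in the window, including M1, M2 and unscheduled values, which SAP 8.1 deliberately includes. Label it as not comparable between pretreatment arms. Add a row from the scheduled visits common to both arms (TP1–TP12, ET/F12M) for the side-by-side reading.

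The cost is SAP wording and one extra table row. No data are discarded: M1, M2 and unscheduled values stay in the existing row, and F7D values falling outside the on-treatment window stay in the by-visit tables and listings. The added row removes the M1/M2 excess but not differences in time on treatment between the arms, which the table should note.

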18.1.13 Subjective opiate withdrawal scale

The answer to each item will be available from the eCRF and thus available in SDTM. The total score will be calculated as sum of the individual answers and available in the ADaM data set. If at least one answer is missing, the total score will be set to missing.

18.2 Sponsor defined alert ranges for laboratory parameters

Potentially clinically important values for laboratory parameters are assessed based on the sponsor defined alert ranges, and can be both, either alert high or alert low values. The sponsor defined alert ranges were defined in the laboratory statement of work and are implemented in the SDTM data. Therefore, they are not repeated here.

18.3 List of statistical output documentation

The statistical output documentation that will be included in the ICTR Section 16.1.9 will contain the original SAS-output for the analysis of the primary endpoint, including sensitivity analyses. Further details will be specified in the Tables Figures and Listings -shell specification document.
